1. STUDY SUMMARY

Provide a brief summary of the proposed research (in language that can be understood by a non-scientist).

Response: Spasmodic dysphonia, or laryngeal dystonia, is a chronic debilitating condition that selectively affects speech production due to involuntary spasms in the laryngeal muscles. SD often extends beyond vocal communication impairment and causes significant occupational disability and life-long social isolation. SD becomes even more incapacitating when it is associated with dystonic voice tremor (VT), which is present in about 1/3 of SD patients and is characterized by the inability to sustain a vowel for more than a few seconds. Current treatment of these disorders is limited to the temporary management of voice symptoms with repeated injections of botulinum toxin into the laryngeal muscles, which, however, are not effective in all SD patients and even less so in combined SD/VT cases. There is, therefore, a critical need to identify alternative therapeutic options that are specifically targeting the pathophysiology of SD and VT. On the other hand, the design and use of such novel therapeutic approaches will be largely unattainable if their central mechanisms of action remain unknown. Our long-term goal is to determine the pathophysiology of SD and related disorders, such as VT, and develop new diagnostic and treatment options for these patients. The objective of this application is to elucidate the primary determinants of clinical response to a novel oral medication, sodium oxybate (Xyrem®), in alcohol-responsive SD and SD/VT patients. This research is innovative because it will use a controlled experimental design that focuses on detailed characterization of primary effects of a novel oral medication, sodium oxybate, for treatment of SD and VT symptoms. The proposed research is significant because it is expected to have broad translational impact on improving the clinical management of patients with SD and VT, opening new therapeutic horizons for treatment of these and similar disorders.

2. SPECIFIC AIMS

List the specific aim(s) and objective (s) of the study (i.e., what does the study hope to accomplish). Include any secondary and exploratory aims and objectives (e.g., biomarkers, genetic analyses).

Response: Determine the clinical response of SD and VT symptoms to sodium oxybate.

3. BACKGROUND AND SIGNIFICANCE

Describe the scientific background and rationale for the study.

- Provide a critical review of the relevant literature and the state of current knowledge on the topic. Discuss deficiencies or gaps in knowledge that make the study worth doing. Include a list of literature cited in an appendix at the end of this protocol.
- Discuss the importance of the topic with respect to scientific knowledge, clinical practice, public health, impact on individuals/community, incidence, prevalence, mortality and morbidity, as applicable.

Response: SD develops in midlife and progresses to become a chronic debilitating condition, which impacts nearly every aspect of a patient's life, causing emotional stress, loss of employment, social embarrassment, and isolation. About 1/3 of SD patients develop so-called dystonic VT, which affects a dystonic body part (i.e., the larynx) and additionally challenges patient's already impaired vocal communication (Kirke et al., 2016). Clinically, the presence of VT in SD patients complicates the accuracy of diagnosis due to the similarities between symptoms of these disorders and shows a poor, if any, response to botulinum toxin treatment (Sulica and Louis, 2010; Gurey et al., 2013). On the other hand, SD symptoms can be managed only temporarily with botulinum toxin injections, although this treatment is not effective in all SD patients (Ludlow et al., 2008; Novakovic et al., 2011). In the clinical setting, a minority of SD and VT patients receive off-label oral medications, such as propranolol, primidone, clonazepam and lorazepam, which, however, provide only mild benefits (Adler, 2000). Other treatment approaches specifically targeting the pathophysiology of these disorders have not been established, leaving a large portion of patients to rely on short-term, and often suboptimal, management of their symptoms with botulinum toxin injections or even remain untreated.

One of the main reasons for the paucity of novel therapeutic options to treat SD and VT is our incomplete understanding of their pathophysiology with respect to treatment outcome. Recent studies by us and others identified SD-characteristic brain functional alterations in the laryngeal sensorimotor cortex, parietal cortex, basal ganglia, thalamus, and cerebellum (Haslinger et al., 2005; Ali et al., 2006; Simonyan and Ludlow, 2010, 2012; Battistella et al., 2016; Termsarasab et al., 2016; Waugh et al., 2016), proposing that SD, similar to other forms of focal dystonia, may represent a large-scale functional network disorder (Battistella et al., 2015). We further identified an extensive overlap between SD and VT functional brain abnormalities, suggesting a similarity of their pathophysiological mechanisms (Kirke et al., 2016). Moreover, common to both SD and SD/VT patients, the severity of voice symptoms correlated with increased brain activity in the putamen and inferior frontal gyrus (Simonyan and Ludlow, 2010, 2012; Battistella et al., 2016; Kirke et al., 2016), suggesting that functional abnormalities in these disorders may be similarly targeted by novel therapeutic options. Taking into account their clinical phenomenology, we found that one of the common clinical traits of SD and VT is the responsiveness of their symptoms to alcohol (Kirke et al., 2015). Thus, by targeting these shared clinical and pathophysiological features of SD and VT, we showed that sodium oxybate (Xyrem®), an oral medication that mimics effects of alcohol, was successful in significantly ameliorating voice symptoms in 82% of alcohol-responsive (ETOH+) patients through direct modulation of abnormal sensorimotor, putaminal and cerebellar brain activity (Simonyan and Frucht, 2013; Kirke et al., 2015; Rumbach et al., 2016). Sodium oxybate is chemically identical to gammahydroxybutyric acid (GHB), a naturally occurring inhibitory neurotransmitter (Waszkielewicz and

Bojarski, 2004); it converts into GABA within the brain (Crunelli et al., 2006) and increases dopamine levels mediated by GABA_B receptors (Gessa et al., 2000; Snead and Gibson, 2005; Keating, 2014). Our current state of knowledge of dystonia pathophysiology suggests that, following its conversion into GABA in SD and SD/VT patients, sodium oxybate likely modulated abnormal brain activity through normalization of the altered balance between excitation and inhibition (Perlmutter et al., 1997; Garibotto et al., 2011; Quartarone and Hallett, 2013; Simonyan et al., 2013), leading to reduction of dystonic symptoms. Thus, based on these data, we anticipate that sodium oxybate may be among the first potent oral medications for treatment of ETOH+ SD and VT that selectively targets the underlying disorder pathophysiology. The drug's benefits will potentially be seen in a large cohort of SD and VT patients because (1) alcohol responsiveness is a common clinical phenomenon in these disorders (Kirke et al., 2015), and (2) improvement of voice symptoms following administration of sodium oxybate is observed in the vast majority of ETOH+ SD and SD/VT patients (Rumbach et al., 2016).

Our initial findings in SD and SD/VT patients are reliable because prior studies of sodium oxybate in patients with various other ETOH+ movement disorders have similarly established satisfactory tolerability and over 50% symptom improvement (Frucht et al., 2005a; Frucht et al., 2005b; Arpesella et al., 2009). However, all these studies have been conducted using an open-label experimental design based on patients' subjective reports of alcohol effects on their symptoms. Likewise, our initial examination of central effects of sodium oxybate in SD and SD/VT patients has also followed an open-label study design. As a consequence, a placebo effect of the drug cannot be ruled out. It is, therefore, critical to perform a standardized test of alcohol challenge for robust stratification of patients into ETOH+ group and conduct a double-blinded, placebo-controlled, randomized, crossover study in order to validate our initial findings of sodium oxybate treatment response and delineate its central effects in ETOH+ SD and SD/VT patients.

Significance of the Expected Research Contribution. Our contribution here entails the detailed understanding of the primary contributing factors that underlie the clinical benefits of sodium oxybate in ETOH+ SD and SD/VT patients. Our rigorous experimental approach will include symptom evaluation based on the objective alcohol challenge test and double-blind, placebo-control, randomized, cross-over study design to identify the primary determinants of sodium oxybate response in ETOH+ SD and SD/VT patients. The expected outcome of these studies will allow for translations from bedside to bench and bedside again, maximizing integration between clinical and basic aspects of this research program. Collectively, the proposed studies have strong scientific premise because they will allow for delineation of the mechanistic aspects of sodium oxybate's effects on SD and VT pathophysiology. As such, successful completion of the proposed studies will establish a muchneeded scientific rationale for the future large clinical trials and the ultimate use of sodium oxybate as a therapeutic option for treatment of SD and VT. This will be especially important for those patients who have suboptimal response to botulinum toxin treatment or forgo it due to personal or medical issues. Thus, this contribution will be significant because it is expected to have a broad translational impact on improving the clinical management of patients with SD and VT. It is further expected that our findings will be equally applicable to the treatment of other forms of ETOH+ dystonia and dystonic tremor. Taken together, the proposed rigorous experimental approach to identify an effective oral medication for SD and SD/VT based on disorder pathophysiology will represent a significant departure from the existing trial-and-error attempts to treat these disorders. It will represent a novel therapeutic approach directed to the treatment of the disorder per se rather than temporary management of voice symptoms as with the current use of botulinum toxin.

4. STUDY DESIGN

Provide a detailed description of the study design (e.g. cross-sectional, stratified, longitudinal, prospective cohort, case-control, randomized, placebo-controlled, masked/double masked, feasibility, pilot, proof-of-concept, etc.).

Explain why this study design is appropriate for this study.

Response: We will employ a double-blind, placebo-controlled, randomized, cross-over study to objectively determine the clinical response to sodium oxybate in ETOH+ SD and SD/VT patients compared to patients with ETOH- SD and SD/VT.

5. SUBJECT INFORMATION

a) Target Enrollment- Specify the number of subjects you plan to enroll and justify why this number is sufficient to achieve adequate power for statistical analysis taking into account anticipated screen failures and drop-outs. Include sample size by cohort if the study has multiple cohorts.

Response: Specific Aim #1: To estimate the number of patients in this study, we reviewed our open-label study, in which sodium oxybate improved voice symptoms in 82.2% (37 out of 45) of ETOH+SD and SD/VT patients (p = 0.001). To our knowledge, no other studies have examined the benefits of sodium oxybate in SD and SD/VT. Using an estimated effect size based on values from this study, a binomial test found that a power of 80% at a significance level of 0.0125 will be obtained with 22 patients for the proposed study. To account for a potential patient dropout based on our prior study, we will recruit up to 35 patients per cohort. The total of recruited patients will be up to 140 (4 cohorts x 35 patients/cohort).

b) If this is a multi-center study and other sites rely on the MEE HSC as the IRB of record, please specify the total number of subjects required by all sites to achieve sufficient power.

Response: N/A

c) Provide justification that the researchers have access to sufficient numbers of eligible subjects to meet target enrollment goals (e.g., researcher's own patients, clinic patients with a specific diagnosis, subjects from previous studies who agree to participate in future studies).

Response: Our research team has access to all patients with dystonia seen at MEEI and MGH/Neurology. All potential subjects will be screened for study participation. Based on our previous experience and studies, our estimation is that about 70% of patients with dystonia may be eligible for participation in this study. In addition, patients will be recruited through the advertisements in the newsletters and websites of the National Spasmodic Dysphonia Association (NSDA) and Dystonia Medical Research Foundation (DMRF), and MEEI flyers. Healthy volunteers can be non-blood relatives of patients. Participants' self-referral will be allowed. Patients seen at MEEI will be asked if they would consider participating in the research study. Subjects from previous studies who agreed to participate in future studies (N~300) will be contacted and screened for eligibility. If the patient is interested, the study purposes and procedures will be explained. If the patient will be willing to participate in the study, he/she will be given the contact information of the

PI and the research team for further information and scheduling of the study procedures. We do not expect any major challenges associated with subject recruitment.

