9. STUDY PROCEDURES

a) Provide a detailed description of all study procedures and intervention(s) each subject and/or cohort will experience. Provide a schedule of visits and the procedures that occur at each visit (e.g., tests, questionnaires, surveys, imaging or other interventions.). If the study also involves standard of care, differentiate between research only procedures and standard of care.

Response:

Determine the clinical response of SD and SD/VT symptoms to sodium oxybate using a double-blind, placebo-controlled, randomized, cross-over study design.

The experimental design includes (1) screening for study eligibility; (2) an objective standardized alcohol challenge test for assessment of symptom responsiveness to alcohol, and (3) a double-blind, placebo-controlled, randomized, crossover study of sodium oxybate. The **primary outcome** will be to determine the response of SD and VT symptoms to sodium oxybate 40 min after administration, compared to placebo. We will recruit the following groups of patients:

- (1) ETOH+ SD and SD/VT who report positive effects of alcohol on their voice symptoms;
- (2) ETOH- SD and SD/VT who report no effects of alcohol on their voice symptoms, and Although our prior studies have shown that sodium oxybate has similar effects in both SD and SD/VT patients as well as in ADSD and ABSD, the inclusion of these patients will allow to capture the entire SD populations and to cross-validate our findings. On the other hand, the inclusion of negative controls with ETOH- SD and ETOH- SD/VT will allow for enhanced explanations of our findings and delineation of the primary factors contributing to the pathophysiology of SD and VT with respect to treatment outcome.

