12. STATISTICAL METHODS

Describe the planned statistical methods including specific tests (e.g., parametric and non-parametric tests, estimation of incidence and prevalence rates, odds ratios, survival/failure analyses, intent to treat analyses). Provide the power calculations used to estimate the proposed sample size. If needed, please consult a biostatistician. (Note: Biostatistical consults are available through Harvard Catalyst.)

Response:

Audio recordings will be de-identified, randomized and blindly rated to count the voice breaks as well as to quantify harshness, breathiness, tremor, and hoarseness using a visual analog scale with three gradation indicators along a 100-mm line (normal, modulates voice, offsets voice), with distance in mm denoting the degree of deviancy from normal, as described earlier (Kirke et al., 2016). Alcohol Challenge Test. All individual measures before and after alcohol intake will be compared using the equation ((Baseline-Alcohol Challenge)/Baseline) \times 100%. To account for potential subjective bias and ensure reliable alcohol effects on voice symptoms, we will consider patients with \geq 10% change of their symptoms from baseline as responsive to alcohol (ETOH+) (Haubenberger et al., 2013; Voller et al., 2014). As a secondary outcome, we will compute Pearson's correlations between symptom scores and brAC measures to examine the baseline and each time point in respect to alcohol content at a corrected p \leq 0.05.

Analysis. The primary outcome within each group will be examined using a linear mixed effect model with treatment (sodium oxybate and placebo) and treatment visits as interacting fixed effects and a per subject random effect at overall $p \le 0.01$ to correct for multiple comparisons. If the interaction between the fixed effects is significant, the difference between treatments will be tested using linear contrasts of least-squares means for the fitted model at $p \le 0.05$ adjusted for multiple comparisons. As a secondary analysis, benefit ratio will be calculated as (sodium oxybate effect – placebo effect) and analyzed using a Friedman test at $p \le 0.01$.

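### Does it matter that section 5a sizes the trial with a binomial test that section 12 never runs?

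*Combined protocol and SAP*

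**What the plan says.** Section 5a starts from the earlier open-label study, in which "sodium oxybate improved voice symptoms in 82.2% (37 out of 45) of ETOH+SD and SD/VT patients". From an effect size based on that study it reports that "a binomial test found that a power of 80% at a significance level of 0.0125 will be obtained with 22 patients". It then raises 22 to at most 35 per cohort to allow for dropout, and adds: "The total of recruited patients will be up to 140 (4 cohorts x 35 patients/cohort").

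Section 9a defines the primary comparison as being to "determine the response of SD and VT symptoms to sodium oxybate 40 min after administration, compared to placebo". It lists two groups, ETOH+ and ETOH-, each covering both SD and SD/VT; the first entry reads "1) ETOH+ SD and SD/VT who report positive effects of alcohol on their voice symptoms".

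Section 12 specifies the main model: "The primary outcome within each group will be examined using a linear mixed effect model with treatment (sodium oxybate and placebo) and treatment visits". These two terms interact, there is a random effect per subject, and the overall level is 0.01. Then: "If the interaction between the fixed effects is significant, the difference between treatments will be tested using linear contrasts of least-squares means", at an adjusted level of 0.05. A Friedman test on the drug-minus-placebo effect is secondary. The only responder threshold, a 10% "change of their symptoms from baseline as responsive to alcohol (ETOH"+), classifies patients at the alcohol challenge and does not define response to the study drug.

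**The concern.** The only statistical support for the cohort size belongs to a test that the plan does not perform. It uses a response rate without a control, although section 3 concedes that the open-label work could not exclude a placebo effect. Neither the null nor the sidedness is given, so a reader cannot tell what 80% refers to.

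Three further points add to the unease:

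- Section 5a works at 0.0125, while section 12 works at 0.01 overall and then at an adjusted 0.05.
- Section 5a counts four cohorts, while section 9a lists two groups, so the number of patients entering each model could be one cohort or two cohorts pooled.
- The alternative hypothesis in section 11 expects no drug effect in ETOH- patients, and an ETOH+ response rate says nothing about what could be detected there.

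If the binomial figure hid a real shortfall, the trial could miss a worthwhile drug-placebo difference in ETOH+ patients, or read too much into a null result in ETOH- patients.

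**Working it through.** **1. Reproducing 22.** Inputs from section 5a: alternative p1 = 37/45 = 0.822, level 0.0125, power 80%. Assumed, because not stated: null p0 = 0.50, one-sided exact test.

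- Size at cut-off 17: P(X ≥ 17 | 22, 0.5) = (26334 + 7315 + 1540 + 231 + 22 + 1)/2^22 = 35443/4194304 = 0.00845, below 0.0125.
- Size at cut-off 16: (35443 + 74613)/4194304 = 0.0262, too large. The rule is therefore to reject at 17 or more.
- Power: P(X ≥ 17 | 22, 0.822) = 0.816. No smaller n reaches 0.80 (n = 21 gives 0.687, n = 19 gives 0.761).

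**2. Sensitivity to what is not stated.**

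- Level 0.01 instead of 0.0125: 0.00845 is also below 0.01, so the cut-off and the power are unchanged.
- Two-sided against 50% (0.00625 per tail): the cut-off is 18 (tail 9109/4194304 = 0.00217), power at 22 is 0.649, and 26 patients are needed (power 0.834).
- One-sided, n = 22, other nulls: power 0.970, 0.919, 0.816, 0.649 and 0.433 for p0 = 0.40, 0.45, 0.50, 0.55 and 0.60.

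**3. The planned comparison.** The documents give no drug-placebo difference, paired standard deviation or placebo rate, so its power cannot be calculated. A paired-t approximation, which ignores the interaction step, gives the difference d (in SDs of the paired difference) detectable with 80% power. It solves P(T with n − 2 df and noncentrality d√n exceeds t at 1 − α/2) = 0.80.

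| Completers | α = 0.01 | α = 0.0125 | α = 0.05, unadjusted |
|---|---|---|---|
| 22 (one cohort) | 0.80 | 0.77 | 0.63 |
| 44 (two cohorts pooled, 2 × 22) | 0.54 | 0.52 | 0.43 |

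Moving from 0.0125 to 0.01 changes the detectable difference by 0.80 − 0.77 = 0.03 SD.

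**4. Responder scenarios.** Exact McNemar test at 0.0125, drug response 82.2%, 22 completers. Placebo rates and within-patient correlation are assumptions.

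| Assumption | Placebo 20% | 30% | 40% |
|---|---|---|---|
| Two-sided, independent responses | 92% | 75% | 50% |
| One-sided, independent responses | 97% | 86% | 65% |
| Two-sided, correlation 0.2 | 99% | 89% | 64% |

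**5. The sign-test reading.** If 82.2% were the share of patients better on drug than on placebo, and the paired differences were normal, the standardized difference would be the normal quantile of 0.822, that is 0.92. Paired-t power with 22 patients at two-sided 0.01 would then be about 92%. The protocol does not state this reading.

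**The case for a change.** The best case for a change is that section 5a should tell a reader what the planned analysis can detect, and it does not. Reproducing 22 takes two assumptions that the protocol leaves out, and a two-sided reading against 50% lowers the power to 64.9%. The increase to 35 is assigned to dropout and is not spare power. A rewritten paragraph would need no more patients.

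Much of this stands: the calculation and the analysis are different things, the null and sidedness are missing, and the figure does not carry over to ETOH- patients. What it does not show is a wrong number. Even on the two-sided reading, 26 completers fit under the ceiling of 35 with dropout of up to (35 − 26)/35 = 25.7%, against the (35 − 22)/35 = 37.1% now implied.

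The different levels are less of a conflict than they look. The adjusted 0.05 is a later step in the sequence of section 12, and 0.0125 equals 0.05/4, which matches four cohorts although the protocol does not give that derivation.

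A paired-t statement would also not be the power of the planned analysis. It leaves out the interaction step, it needs a choice of level that section 12 does not settle in those terms, and an SD unit refers to no particular variable while the outcome comprises voice breaks and four visual analog ratings. Quoting it for 35 or 70 completers would treat a recruitment ceiling as if nobody dropped out.

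**Conclusion.** The mismatch is real, but it is a gap in documentation and calls for no change to the plan. The 22 patients are arithmetically sound on a one-sided exact test against an assumed 50% null (power 81.6%, at 0.0125 and at 0.01 alike). For the planned drug-placebo comparison, the scenarios with 22 completers run from 50% to 99% power depending on assumed placebo rate, sidedness and correlation, so neither under- nor over-powering is shown.

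The mixed model, the comparison and the recruitment ceiling are all in place without the binomial figure. What the trial can say about ETOH- patients will be read from the estimated drug-placebo difference and its confidence interval, which do not depend on the power statement. The analysts will have to say whether each model covers one cohort or SD and SD/VT pooled; on the approximation above that choice moves the detectable difference from about 0.80 to 0.54 SD at 0.01 (22 against 44 completers), but it is a matter of reading section 12 and does not alter the sample size.

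The conclusion rests on the assumed null and sidedness, on the paired-t approximation, and on the absence of any paired standard deviation or placebo rate in the documents. If such figures were available and showed a small standardized difference, the question would deserve another look.
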